8.2.3.4. Subgroup Analysis

The number and proportion of patients who experienced at least one adverse drug reaction will be tabulated for each factor specified in Section 5.4. To evaluate the relationship between patient background factors and the development of adverse drug reactions, the analysis specified in Section 8.1.3 will be performed. Risk ratio and risk difference will not be calculated for concomitant use of steroids or immunosuppressants other than steroids.

The listing of adverse drug reactions will be prepared for contraindicated patients. The number and proportion of patients with adverse drug reactions will be tabulated by SOC and PT as necessary.

8.2.3.5. Exploratory Analysis

The following exploratory analysis will be performed for factors affecting safety.

- In patients treated for ≥180 days in the safety analysis set, the number and proportion of patients with adverse drug reactions by timing of onset of initial event (<180 days, ≥180 days) will be calculated by SOC and PT.
- The number and proportion of patients with adverse drug reactions will be tabulated by SOC and PT by factor with a risk ratio of ≥ 2 or ≤ 0.5 .
- In patients determined to have leukemia as an indication for transplantation, the number and proportion of patients with adverse drug reactions will be calculated by SOC and PT for each of acute lymphocytic leukemia, acute myeloid leukemia, and others (including chronic leukemia).

An additional analysis may be performed as necessary. The exploratory analysis will be reported only when results giving important interpretation are obtained.

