#### 6. RESEARCH QUESTION AND OBJECTIVES

This study is intended to assess the following items, etc. for the safety and effectiveness of Vfend 200 mg for Intravenous Use, Vfend Tablets 50 mg, Vfend Tablets 200 mg, and Vfend Dry Syrup 2800 mg (hereinafter referred to as product) in daily clinical practice for prophylactic administration of this product for invasive fungal infections in children and adults and review the necessity for further special investigation and post-marketing clinical study.

- Unknown adverse reactions including those associated with long-term use
- Occurrence of adverse reactions under actual clinical settings including long-time use
- Factors considered to affect the safety and effectiveness of this product

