2.2. Study Objectives

This surveillance is intended to grasp the following items, etc. for the safety and effectiveness of this product in daily clinical practice for prophylactic administration of this product for invasive fungal infections in pediatric and adults and review the necessity for further special investigation and post-marketing clinical study.

- Unknown adverse reactions including the time of long-term use
- Occurrence of adverse reactions under actual clinical settings
- Factors considered to affect the safety and effectiveness of this product

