8.2.3.1. Adverse Drug Reactions

• All adverse drug reactions

The number and proportion of patients with adverse drug reactions will be tabulated by SOC and PT.

• Serious adverse drug reactions

³: The initial dose and the mean dose (mean maintenance dose) for each of injection and oral agent on and after Day 2 will be calculated for each patient, and administration at doses exceeding the upper limit of the dosage regimen of Vfend or the maximum dose will be considered as overdose.

The number and proportion of patients with serious adverse drug reactions will be tabulated by SOC and PT.

• Details of adverse drug reactions

The number and proportion of patients with adverse drug reactions will be tabulated by SOC and PT for each of the following items and factors.

- Age (1) [\leq 15 years, \geq 15 years]
- Age (2) [≤ 65 years, ≥ 65 years]
- Hepatic dysfunction [absent, present, unknown]
- Renal dysfunction [absent, present, unknown]
- Long-term treatment [<180 days, ≥ 180 days]
- Seriousness [serious, non-serious]
- Expected/unexpected [Expected, unexpected]
- Change in treatment with Vfend [discontinuation, temporarily discontinued, dose reduction, dose increase, no change]
- Outcome [not recovered, recovered with sequela, recovering, resolved/recovered, unknown]

In addition, the number and proportion of patients with serious adverse drug reactions will be tabulated by SOC and PT for each of the following items and factors.

- Age (1) [<15 years, ≥ 15 years]
- Age (2) [<65 years, ≥ 65 years]
- Hepatic dysfunction [absent, present, unknown]
- Renal dysfunction [absent, present, unknown]
- Long-term treatment [<180 days, $\geq 180 \text{ days}$]
- Expected/unexpected [Expected, unexpected]
- Change in treatment with Vfend [discontinuation, temporarily discontinued, dose reduction, dose increase, no change]
- Outcome [not recovered, recovered with sequela, recovering, resolved/recovered, unknown]

If the same adverse event (the same PT) occurs more than once in the same patient, it will be handled as follows in the tabulation of the number of patients with events:

- Seriousness: If both serious and non-serious events are reported, "serious" will be adopted.
- Expected/unexpected: If both expected and unexpected events are reported, "unexpected" will be adopted.
- Number of days to onset: The number of days to the first event will be adopted.

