- Change in treatment with Vfend: If multiple types of change in treatment with Vfend are reported, one of discontinuation, temporarily discontinued, dose reduction, dose increase or no change, in descending order of precedence, will be adopted.
- Outcome: The outcome of the last occurring event will be used.
- Safety specifications

The number and proportion of patients with events will be tabulated. In addition, the number and proportion of patients with safety specifications by change in treatment with Vfend and outcome will be tabulated by SOC and PT.

• Major investigation items

The number and proportion of patients with major investigation items will be tabulated by SOC and PT. In addition, the number and proportion of patients with major investigation items will be tabulated by SOC and PT for each of the following items.

- Change in treatment with Vfend [discontinuation, temporarily discontinued, dose reduction, dose increase, no change]
- Outcome [not recovered, recovered with sequela, recovering, resolved/recovered, unknown]
- Age (1) [<15 years, ≥ 15 years]

Furthermore, in order to examine the difference between patients who discontinued treatment and those who did not by major investigation item, patients with major investigation items will be tabulated by patient background factor, status of discontinuation/completion, concomitant medication, and status of administration.

• Timing of onset of adverse drug reactions

The number of patients with adverse drug reactions will be tabulated by SOC and PT by timing of initial onset of adverse drug reactions. Categories of timing of onset will be every 30 days. However, if there are many adverse drug reactions that occur at an early stage, the analysis will be performed by subdividing the category of the first 30 days as necessary. Major investigation items will be analyzed in the same manner.

For major investigation items, time to event onset will be summarized for each patient in accordance with Section 8.1.4 with the initial onset of the major investigation item considered as an event. Patients without adverse drug reactions will be right-censored after the observation period + follow-up period (28 days) of this study.

• Relationship between concomitant medications and development of adverse drug reactions

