8.2.4.5. Exploratory Analysis

The following exploratory analysis will be performed for factors affecting effectiveness.

 Listings by presence/absence of onset of invasive fungal infections and presence/absence of successful prophylaxis of invasive fungal infections will be prepared by factor with a risk ratio of ≥2 or ≤0.5.

An additional analysis may be performed as necessary. The exploratory analysis will be reported only when results giving important interpretation are obtained.

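### Exploratory analyses listed in the SAP, including the only planned late-onset proportion among long-term users, can go unreported depending on their results

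*SAP*

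**What the plan says.** SAP 8.2.3.5 opens with a commitment: "The following exploratory analysis will be performed for factors affecting safety". Three items follow.

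- In patients treated for at least 180 days, adverse drug reactions "by timing of onset of initial event (<180 days, ≥180 days) will be calculated by SOC and PT".
- Adverse drug reactions by SOC and PT for each factor with a risk ratio of at least 2 or at most 0.5.
- In patients transplanted for leukaemia, adverse drug reactions by leukaemia type.

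The section then allows additional analyses and ends: "The exploratory analysis will be reported only when results giving important interpretation are obtained".

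SAP 8.2.4.5 has the same structure for effectiveness. It begins "The following exploratory analysis will be performed for factors affecting effectiveness", lists patient listings for factors passing the same risk-ratio screen, allows additions, and repeats the reporting sentence.

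SAP Section 3 says that every analysis specified in the plan is carried out at the final analysis. It does not say that every one is reported.

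Long-term use appears in the first listed objective of both documents: "Unknown adverse reactions including those associated with long-term use" (Protocol Section 6) and "Unknown adverse reactions including the time of long-term use" (SAP 2.2). The third objective concerns factors affecting safety and effectiveness.

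**The concern.** The rule makes reporting depend on the result, and nothing in the SAP says what makes a result important. It is attached to analyses fixed in advance, so a reader who finds one missing from the report cannot tell whether it was unremarkable or was left out for some other reason. Those that do appear will have been chosen because they were striking.

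For a post-marketing safety study this runs against the purpose. A finding that few or no reactions first appear late among long-term users is an answer to the first objective, and it is the kind of result the rule would tend to leave out.

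**Working it through.** No figure in the plan bears on the reporting rule, so the check is a comparison of sections: what is conditional, and what unconditional output could stand in for it.

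**Step 1: unconditional outputs on long-term use**

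- SAP 8.2.2: treatment period in 30-day bands, and the number treated for less than 180 days and for 180 days or more.
- SAP 8.2.3.1, the breakdown by patient factor: "The number and proportion of patients with adverse drug reactions will be tabulated by SOC and PT for each of the following items and factors". The list includes long-term treatment (below 180 days, 180 days or more). The same split is planned for serious reactions.
- SAP 8.2.3.1, timing of onset: counts by SOC and PT. "Categories of timing of onset will be every 30 days". Kaplan-Meier time to onset is planned for the major investigation items only.
- SAP 8.2.3.4 with 5.4: any adverse drug reaction by long-term treatment and by treatment duration, with risk ratio and risk difference where the minimum-count rule in 8.1.3 allows.
- SAP 8.2.4.1 and 8.2.4.2: infection rate and success rate by long-term treatment, with 95% confidence intervals.
- SAP 8.2.3 and Section 9: all reported events in listings, and a listing of treatment status.

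**Step 2: do these replace the first item of 8.2.3.5?**

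- The 8.2.3.1 split by long-term treatment sorts patients by how long they were treated, not by when the reaction began. A reaction on Day 5 in a patient treated for 200 days falls in the column for 180 days or more.
- The 8.2.3.1 onset table does sort by onset time, but it gives numbers of patients over the whole safety set, with no proportion and no denominator restricted to long-term users.
- The populations are close but not identical. Events are tabulated to 28 days after treatment (8.2.3), so an onset at Day 180 or later can come from a patient treated for about 180 − 28 = 152 days or more. Patients treated for roughly 152 to 179 days can therefore enter the late rows.

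The first item of 8.2.3.5 is thus the only planned table giving the proportion with late first onset among patients treated for at least 180 days, by SOC and PT.

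**Step 3: the other conditional items**

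- Leukaemia type: SAP 5.4 treats leukaemia as one class, so the breakdown is planned only in 8.2.3.5.
- Flagged factors: the factor-level results are unconditional (8.2.3.4, 8.2.4.4). The SOC/PT tables and patient listings that follow from the screen are conditional. They have already passed a stated filter (risk ratio at least 2 or at most 0.5) and then meet a second, undefined one.

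**Step 4: what a null would carry (illustration)**

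The documents do not say how many patients will be treated for 180 days or more, so n is an assumption. With zero late reactions in n patients, the upper limit of the exact two-sided 95% interval is 1 − 0.025^(1/n).

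- n = 20: 1 − 0.025^(1/20) = 16.8%
- n = 40: 1 − 0.025^(1/40) = 8.8%
- n = 80: 1 − 0.025^(1/80) = 4.5%

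SAP 8.2.3.5 plans only numbers and proportions, so these limits are not themselves suppressed outputs. They show that a zero says something measurable.

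**The case against.** Four arguments can be made for leaving the text alone.

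1. **The sentence may cover only unplanned work.** It directly follows the one allowing additional analyses, so this may be the intent. But its subject repeats the section heading and the lead-in to the listed items, and nothing limits it to additions. If the narrow reading was meant, the fix only says so.

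2. **Long-term use is well covered elsewhere.** This stands. A reader might infer that null findings on long-term use disappear from the report altogether; the unconditional tables in 8.2.2, 8.2.3.1, 8.2.3.4, 8.2.4.1 and 8.2.4.2 and the listings rule that out. A complete absence of late reactions could even be inferred: if the onset table shows no first onset from Day 180, there was none among long-term users either, and 8.2.2 supplies the denominator. When some late reactions do occur, the proportion has to be rebuilt by linking the reaction and treatment listings.

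3. **The effectiveness part is thin.** This also stands. SAP 8.2.4.5 contains no dedicated long-term-use analysis. All effectiveness subgroup results are unconditional, as is the listing of patients evaluated for effectiveness. Only the listings arranged by flagged factor are at risk.

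4. **The study is not confirmatory.** SAP 4.1 sets no significance level and treats P values as descriptive, so no error rate is at stake. That is right, but selective reporting distorts descriptive tables too.

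**Conclusion.** The point holds in a limited form. As written, SAP 8.2.3.5 and 8.2.4.5 attach a result-dependent reporting rule, without a criterion, to analyses specified in advance. What it can drop is the late-onset proportion among patients treated for at least 180 days, the leukaemia-type tables, and the follow-up tables and listings for flagged factors. No main safety or effectiveness analysis is affected, and no objective is left wholly unanswered.

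The conclusion rests on reading the closing sentence as applying to everything under its heading. The upper limits of 16.8%, 8.8% and 4.5% rest on assumed numbers of long-term patients and are illustrative only. They should not be read as information that the rule would hide, since a zero could be recovered from the unconditional tables.

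**What to change.** In SAP 8.2.3.5 and 8.2.4.5, state that all analyses listed there are reported whatever the result. Reword the closing sentence in each so that it applies only to additional analyses not listed in the SAP.

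Section 3 already requires the listed analyses to be run at the final analysis, so there is no extra data collection or computation. The cost is a change of wording in two sections and a few more tables in an appendix.

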8.2.4. Effectiveness Analysis

8.2.4.1. Proportion of Patients Who Developed Invasive Fungal Infections (IFI rate)

In the effectiveness analysis set, the proportion of patients who developed invasive fungal infections (%) and its 95% confidence interval will be calculated. The calculation formula is shown below.

Proportion of patients who developed invasive fungal infections (%) = [(number of patients with proven diagnosis + number of patients with probable diagnosis)/number of patients for effectiveness analysis excluding undeterminable patients] \times 100

For each of the following factors specified in Section 5.4, the same subgroup analyses will be performed.

- Indication for transplantation
- Objective of treatment [primary prophylaxis, secondary prophylaxis]
- Age (1) [\leq 15 years, \geq 15 years]
- Age (2) [<65 years, ≥ 65 years]
- Hepatic dysfunction [absent, present, unknown]
- Renal dysfunction [absent, present, unknown]
- Long-term treatment [<180 days, ≥180 days]

8.2.4.2. Proportion of Patients with Successful Prophylaxis of Invasive Fungal Infections (Success rate)

In the effectiveness analysis set, the proportion of patients with successful prophylaxis of invasive fungal infections (%) and its 95% confidence interval will be calculated. The calculation formula is shown below.

Proportion of patients with successful prophylaxis of invasive fungal infections (%) = (number of patients without onset of invasive fungal infections/number of patients for effectiveness analysis excluding undeterminable patients) \times 100

For each of the following factors specified in Section 5.4, the same subgroup analyses will be performed.

- Indication for transplantation
- Objective of treatment [primary prophylaxis, secondary prophylaxis]
- Age (1) [<15 years, ≥ 15 years]
- Age (2) [<65 years, ≥ 65 years]
- Hepatic dysfunction [absent, present, unknown]
- Renal dysfunction [absent, present, unknown]
- Long-term treatment [<180 days, $\geq 180 \text{ days}$]

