# 7.2.6. Observation period

The observation period shall start on the day the administration of this product begins and ends on the day the administration is completed; provided that the patients will be followed until the last day of the investigation period as long as possible if the administration period prolongs.

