#### Effectiveness perspectives:

The successful rate of prophylaxis at Day 100 in the phase 3 study of prophylactic administration (study A1501073) was 54.3% (121/223 patients) and the successful rate of prophylaxis at Day 180 was 48.9% (109/223 patients). Presuming that the 50% prophylactic effect can be obtained at Day 180 by referring to the above results, the 95% CI will be 40 - 60% if the target sample size is set to be 100 patients and 43-57% if the target sample size is set to be 200 patients. The prophylactic effect can be confirmed at the estimate accuracy of about  $\pm 10\%$  if 100 patients for whom this product is administered for prophylaxis of invasive fungal infections are accumulated and that of about  $\pm 7\%$  if 200 patients are accumulated.

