#### (2) Effectiveness analysis

The proportion of patients who developed invasive fungal infections (the number of patients with proven diagnosis + the number of patients with probable diagnosis/number of patients for effectiveness analysis excluding undeterminable patients  $\times$  100), proportion of patients with successful prophylaxis of invasive fungal infections (the number of patients without onset of invasive fungal infections/the number of patients for effectiveness analysis excluding undeterminable patients  $\times$  100), and each 95% CI will be calculated for effectiveness analysis set. Also, the analysis using the survival analysis method (Kaplan-Meier method) will be performed.

Detailed methodology for summary and statistical analyses of data collected in this study will be documented in a Statistical Analysis Plan (SAP), which will be dated, filed and maintained by the Sponsor. The SAP may modify the plans outlined in the protocol; any major modifications of primary endpoint definitions or their analyses would be reflected in a protocol amendment.

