The successful rate of prophylaxis at Day 100 in the phase 3 study of prophylactic administration (study A1501073) was 54.3% (121/223 patients) and the successful rate of prophylaxis at Day 180 was 48.9% (109/223 patients). Presuming that the 50% prophylactic effect can be obtained at Day 180 by referring to the above results, the 95% CI will be 40-60% if the target sample size is set to be 100 patients and 43-57% if the target sample size is set to be 200 patients. The prophylactic effect can be confirmed at the estimate accuracy of about $\pm 10\%$ if 100 patients for whom this product is administered for prophylaxis are accumulated and that of about $\pm 7\%$ if 200 patients are accumulated.

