6.2. Effectiveness Endpoints

• Presence or absence of invasive fungal infections: The onset of invasive fungal infections during the observation period will be judged. If the treatment with this product is continued at the completion of

study period, the onset of invasive fungal infections until the completion of study period will be judged.

- Without onset
- With onset
- Indeterminate
- In case of "with onset" of invasive fungal infections, it will be classified as follows according to the diagnostic criteria of the European Organization for Research and Treatment of Cancer/Mycoses Study Group (EORTC/MSG).
 - Proven diagnosis*
 - Probable diagnosis^{**}
 - Possible case***

*: Proven diagnosis: Patients who have clinical symptoms and findings of inflammation caused by mycosis and the causative fungi are proved from the histological diagnosis of the focus of infection or mycological diagnosis from the sterile site, etc.

: Probable diagnosis: At least one host factor + one clinical criterion + one mycological criterion *: Possible case: At least one host factor + meeting one clinical criterion but no mycological criterion

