8.1.3. Analysis of Binary Data

The frequency and proportion will be calculated. If the confidence interval of proportion is calculated, two-sided 95% confidence interval (exact method) will be calculated.

If the proportion is compared between subgroups, risk ratio and its 95% confidence interval, and risk difference and its 95% confidence interval will be calculated. In addition, risk ratio and its 95% confidence interval will be graphically presented (see Appendix 2). If the number of patients in at least one category compared is \leq 5, the number of patients and proportion will be calculated but risk ratio and its 95% confidence interval, and risk difference and its 95% confidence interval will not be calculated.

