8.1.4. Analysis of Period Data (Time to Event Onset)

The median, first quartile, and third quartile by Kaplan-Meier method will be calculated. In addition, Kaplan-Meier plots will be prepared.

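### The ±10%/±7% precision is stated for success at Day 180, but the plan tabulates no Day-180 infection-free probability with a confidence interval

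*SAP*

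**What the plan says.** **Size rationale.** Protocol 7.5.2 (Effectiveness perspectives) cites success in study A1501073 of 54.3% (121/223) at Day 100 and 48.9% (109/223) at Day 180. It continues: "Presuming that the 50% prophylactic effect can be obtained at Day 180 by referring to the above results". SAP 2.1 repeats this and states that "the 95% CI will be 40-60% if the target sample size is set to be 100 patients", with 43-57% for 200 patients. Both documents summarise the precision as about ±10% and ±7%.

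**Planned success rate.** SAP 8.2.4.2 uses "number of patients without onset of invasive fungal infections/number of patients for effectiveness analysis excluding undeterminable patients", times 100, and Protocol 7.7 has the same formula. For the interval, SAP 8.1.3 says "two-sided 95% confidence interval (exact method) will be calculated". The formula names no time point.

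**Window.** SAP 6.2 says: "The onset of invasive fungal infections during the observation period will be judged". Under Protocol 7.2.6 that period starts on the first day of administration and "ends on the day the administration is completed". If treatment continues, follow-up runs to the end of the investigation as far as possible.

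**Kaplan-Meier.** Protocol 7.7 says: "Also, the analysis using the survival analysis method (Kaplan-Meier method) will be performed". SAP 8.1.4 fixes the output: "The median, first quartile, and third quartile by Kaplan-Meier method will be calculated. In addition, Kaplan-Meier plots will be prepared". SAP 8.2.4.3 applies this to two event definitions (proven plus probable, and any onset) and censors patients without onset at the end of treatment.

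**Other uses of 180 days in effectiveness.** SAP 8.2.4.1 and 8.2.4.2 split patients at 180 days of treatment. SAP 5.4, applied through 8.2.4.4, also groups them by treatment duration in 30-day bands up to 180 days and above.

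**The concern.** The quantity whose precision justifies the size is success at a fixed day. The quantity to be tabulated is the proportion without onset while on treatment, whatever the length of treatment. The two agree only if every analysed patient's status at Day 180 is known, or by coincidence of treatment lengths.

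The Kaplan-Meier analysis could supply the Day-180 value. Its numerical output, however, is a set of times (median and quartiles), not a probability at a given day.

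Two things are at stake. A reader of the size rationale may take the reported success rate for the Day-180 rate. The stated ±10/±7 points may also be taken as the precision of a Day-180 estimate, which it is not when patients are censored before then.

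**Working it through.** **1. Reproduce the plan's figures.** Inputs are p = 0.50 and n = 100 or 200 (Protocol 7.5.1, 7.5.2), two-sided 95%. Half-width = 1.96 × √(p(1−p)/n).

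- n = 100: 1.96 × √(0.25/100) = 9.8 points. The exact interval for 50/100 is 39.8-60.2%.
- n = 200: 1.96 × √(0.25/200) = 6.9 points. The exact interval for 100/200 is 42.9-57.1%.

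Both agree with the stated 40-60% and 43-57%. The arithmetic is right for a binomial proportion in which every patient's outcome is known.

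**2. Can all patients reach Day 180?** Follow-up for onset stops with treatment. Registration runs to August 2018 and the investigation to October 2018 (Protocol 7.2.4). Taking 31 October 2018 as the last day, a patient starting after about 5 May 2018 cannot reach Day 180. That is 118 of the 1,065 days from 1 October 2015 to 31 August 2018, about 11% of the registration window.

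**3. Illustrate the gap.** The documents give no distribution of treatment duration, so what follows is assumed: constant infection hazard λ, independent exponential treatment duration with stopping rate μ = ln 2 / median, and no calendar cut-off. The 50% planning figure is read as 50% infection-free at Day 180, so λ = ln 2 / 180.

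- Expected crude success rate = μ/(λ+μ).
- Greenwood variance of the Kaplan-Meier estimate at Day 180 = (S²/n) × λ/(λ+μ) × (exp((λ+μ) × 180) − 1), with S = 0.5. Half-width = 1.96 × its square root.
- Expected number at risk at Day 180 = n × exp(−(λ+μ) × 180).

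Worked case, median 60 days: λ/(λ+μ) = 0.25 and exp((λ+μ) × 180) = 16. The crude rate is 75%. For n = 100 the variance is 0.25/100 × 0.25 × 15 = 0.009375, giving a half-width of 19.0 points.

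| Median treatment (days) | Crude success rate | Day-180 half-width, n=100 / n=200 (points) | At risk at Day 180, n=100 / n=200 |
|---|---|---|---|
| 60 | 75.0% | ±19.0 / ±13.4 | 6.2 / 12.5 |
| 90 | 66.7% | ±15.0 / ±10.6 | 12.5 / 25.0 |
| 120 | 60.0% | ±13.4 / ±9.5 | 17.7 / 35.4 |
| 180 | 50.0% | ±12.0 / ±8.5 | 25.0 / 50.0 |

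The true Day-180 value is 50% in every row. At 150/200 observed, the exact 95% CI is 68.4-80.8%, which excludes 50%.

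**4. If infection is less common.** Take 90% infection-free at Day 180, an assumed value that is not in the documents, so λ = −ln(0.9)/180. The crude rate becomes 95.2, 92.9, 90.8 and 86.8% at the same four medians, within about 5 points of the true value and on either side of it. The Day-180 half-widths at medians 60, 90 and 120 are ±10.9/±7.7, ±8.7/±6.2 and ±7.8/±5.5 points. From a median of 90 days upward these stay inside ±10/±7.

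**The case against.** The strongest reply is that the precision statement suits the analysis actually planned. A proportion of 50% gives essentially the widest binomial interval, so ±10/±7 points is close to a ceiling for the crude rate when 100 or 200 patients are determinable, whatever the time point. This stands. A reader might infer that the study is too small for its effectiveness analysis; the documents do not support that.

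Second, a reader might infer that the report will say nothing about Day 180. That goes too far. Both Kaplan-Meier plots will show the value graphically, and the 30-day duration bands will give counts with and without onset. But the plot comes with no specified CI or number at risk. The bands, like the 180-day split, classify patients by achieved exposure: someone who stops early because of infection falls in a short-duration band. Treatment may also continue after onset when its purpose changes (Protocol 7.3.5), so the bands do not date onset either. Neither grouping gives a Day-180 estimate with a CI for the cohort. SAP 8.2.4.5 permits further analyses but commits to none.

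Third, the size of the gap comes from a model. This stands as well. A bias of 25 points is one assumed scenario, not a finding. A reader might likewise infer that the planned quartiles will never be reached; that depends on a low infection rate which the documents do not give.

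Fourth, the documents do not define success in study A1501073. If it meant more than absence of infection, an infection-free probability would match the 50% in time point but not in content. Relabelling resolves the mismatch either way.

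**Conclusion.** The point holds in a limited form. The size rationale attributes ±10/±7 points to success at Day 180, and the plan tabulates no Day-180 infection-free probability with a confidence interval. The half-widths themselves are correct for the crude on-treatment proportion, given about 100 or 200 determinable patients.

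How far the crude rate would lie from the Day-180 value cannot be settled from the documents. Under the stated assumptions the difference runs from 25 points to none in the 50% case. In the 90% case it is about 5 points or less and can change sign. Those figures rest on constant hazard, exponential treatment duration independent of infection, and reading 50% success as 50% infection-free.

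Severity is minor. SAP 4.1 treats all tests as exploratory, SAP 4.2 has no decision rule, and no comparison with the 48.9% is planned.

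**What to change.** - In SAP 8.1.4 and 8.2.4.3, add Kaplan-Meier infection-free probabilities at Day 100 and Day 180 with 95% CI and numbers at risk, for both planned event definitions. The any-onset curve is the one that corresponds to the 8.2.4.2 success definition.
- In SAP 8.2.4.2, label the success rate as on-treatment with no fixed time point.
- In SAP 2.1 and Protocol 7.5.2, state that ±10%/±7% apply to that crude proportion, or to Day 180 only with complete follow-up.

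The cost is some wording and one table. Administration period (Protocol 7.3.2) and date of onset (Protocol 7.3.6.1) are already collected, and no planned analysis is replaced. There are three downsides. The stated Day-180 precision may be less favourable than ±10/±7. Few patients may be at risk at Day 180 if treatment is short, which the numbers at risk would show. Censoring at the end of treatment may be informative, a weakness that the added estimates share with the curves already planned.
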